9.5.2. SAS Code for Efficacy Analyses

9.5.2.1. SAS Code for the Primary Efficacy Endpoint

The primary efficacy endpoint is survival (based on all-cause mortality) at Day 29 and will be compared between the 2 treatment groups using a 1-sided MH test of the difference in 2 proportions stratified by intubated or not intubated on Day 1. The basic SAS code for this is:

```
Proc freq data=adeff;  
    tables intub*trt01p*surv / commonriskdiff (test=mh column=2);  
run;
```

where intub is the randomization stratification factor, trt01p is the patient's randomized treatment group, and surv is the survival status (0=death, 1=survive).

For the primary efficacy analysis, missing data will be imputed using a multiple imputation approach assuming the data are MAR and using a logistic regression model. The basic SAS code for this is:

```
Proc mi data=adeff out=outmi seed=1306528 nimpute=pctmissing;  
    class trt01p intub sex comorbid surv;  
    var trt01p intub sex age comorbid surv;  
    monotone logistic(surv = trt01p intub sex age comorbid / details);  
run;
```

where intub is the randomization stratification factor, trt01p is the patient's randomized treatment group, age is patient age on Day 1, sex is the patient's sex, and comorbid is a dichotomous variable to indicate if the patient has at least one pre-existing condition at baseline

(diabetes mellitus, obesity, respiratory condition, and/or coronary artery disease) and surv is the survival status (0=death, 1=survive).

The imputed data sets will then be analyzed by imputation using the MH method described above and the PROC MIANALYZE procedure will be used to generate valid statistical inferences about these parameters. The basic SAS code for this is:

```
Proc mianalyze data=commonpdifftests;  
    modeleffects riskdifference;  
    stderr stderr;  
  
run;
```

A sensitivity analysis of the primary endpoint will use a delta-adjustment tipping point approach where the missing survival data for patients randomized to ravulizumab + BSC group are imputed by shifting the survival probability of the observed patients downward by delta. For each value of delta, the treatment effect will be determined, and the value of delta for which the nominal 1-sided p-value crosses 0.025 will be considered as the ‘tipping point’ in the sense that the positive conclusion drawn from the primary analysis is reversed. The basic SAS code for this is:

```
Proc mi data=adef out=outmi seed=1306528 nimpute=pctmissing;  
    class trt01p intub sex comorbid surv;  
    var trt01p intub sex age comorbid surv;  
    monotone logistic(surv = trt01p intub sex age comorbid / details);  
    mmar adjust (surv(event='1') / shift=delta adjustobs=(trt01p='Ravulizumab + BSC'));  
  
run;
```

where delta is the shift parameter for the imputed values of survival for patients randomized to ravulizumab + BSC group.

A sensitivity analysis of the primary endpoint will use a log-rank test including strata for the randomization stratification factor. The basic SAS code for this is:

```
proc lifetest data = adtte;  
    time aval*cnsr(1);  
    strata intub / group=trt01p;  
  
run;
```

where trt01p is a variable that indicates the patient’s randomized treatment group, aval is a variable for the patient’s time in analysis period at time of death or censoring, cnsr is the censoring variable (1 = no event (censored), 0= event), intub is the randomization stratification factor.

The hazard ratio and risk reduction will be estimated from a stratified Cox proportional hazards model. The basic SAS code for this analysis is:

```
proc phreg data = adtte;
```

```
class trt01p intub;  
model aval*cnsr(1) = trt01p;  
strata intub;  
hazardratio trt01p;  
run;
```

A sensitivity analysis of the primary endpoint will use a proportional odds model. The basic SAS code for this analysis is:

```
proc logistic data=adtte;  
class trt01p intub / param=glm;  
model survcat=trt01p intub;  
oddsratio trt01p;  
lsmeans trt01p / diff;  
run;
```

where intub is the randomization stratification factor, trt01p is the patient's randomized treatment group, and survcat is the survival category (1 = death, 2 = alive and in ICU, 3 = alive and discharged from ICU).

A sensitivity analysis of the primary endpoint will use a multivariate logistic regression analysis. The SAS macro LR ([Ge, 2011](#)) will be used for this analysis. The following macro call will be used:

```
%LR(data=adef, var1=age, var2=trt01p sex region intub, p1=1, p2=4, resp=surv, ntrt=1);
```

A sensitivity analysis of the primary endpoint will use a multivariate Cox proportional hazards model. The basic SAS code for this analysis is:

```
proc phreg data = adtte;  
class trt01p sex region intub;  
model aval*cnsr(1) = trt01p age sex region intub;  
hazardratio trt01p;  
run;
```

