#### **8.4.12. Early Termination**

If a patient is discontinued from the study during the Primary Evaluation Period (ie, from Day 1 through Day 29), the patient should present for the Early Termination visit, to be conducted as specified in the SoA ([Table 1](#)). The patient will be contacted via telephone on Day 29 to assess health status (eg, survival, mechanical ventilation, hospitalization, intensive care unit, and dialysis).

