### 9.2. Sample Size Determination

A sample size of 243 patients (162 ravulizumab + BSC, 81 BSC alone) is required to ensure at least 90% power and detect an improvement in survival from 60% in the BSC alone group to 80% in the ravulizumab + BSC group at Day 29.

This sample size calculation assumes:

- 1-sided Z-test of the difference in 2 proportions,
- Type I error = 0.025,
- Pooled variance,
- 2:1 randomization on the 2 treatment groups,

- One interim analysis at 50% information which will be after collecting primary efficacy data on approximately 122 patients. The early stopping boundaries for efficacy and futility (nonbinding) will be constructed using  $\alpha$ -spending function as Lan-DeMets spending function with O’Brien-Fleming flavor and  $\beta$ -spending function as Gamma(-4) (Lan, 1983; Hwang, 1990).

Considering a nonevaluable rate of 10%, this study is planned to randomize approximately 270 patients (180 ravulizumab + BSC, 90 BSC alone).

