7.4. Interim Analysis

The primary null hypothesis that is being tested is that there is no difference in survival between 2 treatment groups (ravulizumab + BSC and BSC alone) as measured by the difference in the proportions surviving at Day 29 between the 2 treatment groups.

The alternative hypothesis is that ravulizumab + BSC will improve survival by 20% at Day 29 compared to BSC alone.

Hence, the treatment effect is $\delta = \pi_{\text{rav+BSC}} - \pi_{\text{BSC}}$, where π = proportion of patients surviving on study arm and they hypotheses are

Null hypothesis $H_0: \delta = 0$

Alternative hypothesis $H_1: \delta > 0$ (specifically 0.2).

With this treatment effect, an overall 1-sided Type I error of 0.025 and 2:1 randomization, approximately 243 patients will be required to achieve at least 90% power. Considering 10% nonevaluable subjects, a total of 270 patients will be enrolled in the study.

A pre-planned interim analysis for efficacy and futility will be conducted when approximately 50% of the information is available, that is after approximately 122 patients have completed Day 29. If the stopping criteria are met, the study may be terminated early for efficacy or futility depending on which stopping boundary is crossed.

The early stopping boundaries for efficacy and futility (non-binding) will be constructed using α -spending function as Lan-DeMets (O'Brien-Fleming) spending function, published by [Lan and DeMets \(1983\)](#) and β -spending function as Gamma(-4) that was first published by [Hwang et al \(1990\)](#).

Use of these spending functions ensures the control of Type I error to 0.025.

The p-value efficacy and futility boundaries for the interim analysis with 122 patients are 0.0016 and 0.5016. The [1-sided] p-value from the t-test statistic based on the results from combining all imputed datasets for overall inference (ie, from PROC MIANALYZE) will be compared with these stopping boundaries. The study will be terminated and ravulizumab will be declared as being statistically significant and more efficacious than BSC if the nominal [1-sided] p-value is less than 0.0016 and the study can be terminated for futility if the nominal [1-sided] p-value is greater than 0.5016.

Table 3: Stopping Boundaries

Analysis	Efficacy Boundary (p-value scale)	Futility Boundary (p-value scale)
Interim (~122 patients)	0.0016	0.5016
Final (243 patients)	0.0245	0.0245

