9.5.2.2. SAS Code for the Secondary/Exploratory Efficacy Endpoints

9.5.2.2.1. Analysis of Covariance (ANCOVA)

For some secondary endpoints, an ANCOVA model will be used to compare the 2 treatment groups. The basic SAS code for this analysis is given by:

```
proc glm data = adef;  
class trt01p intub;  
model aval = trt01p age intub / solution;
```

```
lsmeans trt01p / cl diff stderr;  
run;
```

where aval is the number of days.

Missing data will be imputed using a multiple imputation approach assuming the data are MAR and using a regression model. The basic SAS code for this is:

```
Proc mi data=adeff out=outmi seed=1306528 nimpute=pctmissing round=. . . . 1 maximum=. . .  
.. 29 minimum=. . . . 1;  
class trt01p intub sex comorbid;  
var trt01p intub sex age comorbid aval;  
monotone reg(aval = trt01p intub sex age comorbid / details);  
run;
```

If an imputed value for a patient is less than the observed number of days until dropout, then the observed number will be used. The imputed data sets will then be analyzed by imputation using the ANCOVA method described above and the PROC MIANALYZE procedure will be used to generate valid statistical inferences about these parameters. The basic SAS code for this is:

```
Proc mianalyze data=parameterestimates;  
modeffects estimate;  
stderr stderr;  
run;
```

A sensitivity analysis will use a delta-adjustment tipping point approach where the missing data for patients randomized to ravulizumab + BSC group are imputed by shifting the number of days for the observed patients downward by delta. For each value of delta, the treatment effect will be determined, and the value of delta for which the nominal 2-sided p-value crosses 0.05 will be considered as the ‘tipping point’ in the sense that the positive conclusion drawn from the primary analysis is reversed. The basic SAS code for this is:

```
Proc mi data=adeff out=outmi seed=1306528 nimpute=pctmissing round=. . . . 1 maximum=. . .  
.. 29 minimum=. . . . 1;  
class trt01p intub sex comorbid;  
var trt01p intub sex age comorbid aval;  
monotone reg(aval = trt01p intub sex age comorbid / details);  
mmar adjust (aval / shift=delta adjustobs=(trt01p='Ravulizumab + BSC'));  
run;
```

where delta is the shift parameter for the imputed values of days for patients randomized to ravulizumab + BSC group.

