9.5.2.2.2. Mixed Model for Repeated Measures (MMRM) Analysis

For some secondary endpoints, the analysis of changes over time involves an MMRM analysis. The basic SAS code for this analysis is given by:

```
proc mixed data = adeff method = reml;
  class subjid avisit trt01p intub;
  model chg = trt01p avisit trt01p*avisit base age intub / ddfm = kr solution;
  repeated avisit / type=un subject=subjid;
  lsmeans trt01p*avisit / cl diff;
  where 1 < avisitn;
run;
```

where trt01p is a variable that indicates the patient's randomized treatment group, subjid is the patient variable, avisit is the study day variable (0 representing Day 1), base is the value at baseline, age is patient age on Day 1, chg is the change from baseline at a particular visit, and intub is the randomization stratification factor.

The following illustrates the sensitivity analysis for missing data using the control-based approach, where for patients who discontinued treatment, responses after treatment discontinuation for both treatment groups will be imputed with multiple imputation methodology based on the response for BSC alone patients. Markov Chain Monte Carlo (MCMC) imputation method will be used to fill in the intermittent missing values under the assumption of MAR and generate a monotone pattern. Subsequently, multiple imputation will be performed at each visit sequentially, using a regression method obtained from BSC alone patients with terms for baseline score, the randomization stratification variable, and previous visits. After obtaining complete data sets for each visit, these complete data sets will be analyzed using MMRM analysis, and inferences from each complete data set will be combined to obtain an overall test statistic for treatment effect. The basic SAS code for this is:

```
Proc mi data=adefft out=monotone seed=1306528 nimpute=pctmissing;
  by trt01p;
  mcmc impute=monotone;
  var intubn base Day5 Day10 Day15 Day22 Day29;
run;
```

where trt01p is a variable that indicates the patient's randomized treatment group, base is the value at baseline, Day5 – Day29 are the changes from baseline at a particular visit, and intubn is a dummy variable for the randomization stratification factor.

The following is a partial SAS code for the BSC alone-based imputation at Day X:

```
Proc mi data=monotone out=outmi seed=1306539 nimpute=1;
  by _imputation_;
  class trt01p intub;
```

```
var intub base Day5 Day10 Day15 Day22 Day29;  

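### Fix the number of imputations at 1000 instead of tying it to the percentage missing, so that the pooled survival p-value does not depend visibly on the seed; relabel age as age on Day 1

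*SAP*

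**What the plan says.** **Primary endpoint.** SAP 9.5.2.1 imputes missing survival under MAR with "Proc mi data=adeff out=outmi seed=1306528 nimpute=pctmissing". Its tipping-point analysis uses "Proc mi data=adef out=outmi seed=1306528 nimpute=pctmissing".

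**Secondary endpoints.** SAP 9.5.2.2.1 has two calls, one for the ANCOVA imputation and one for its tipping-point analysis, both beginning "Proc mi data=adeff out=outmi seed=1306528 nimpute=pctmissing round". SAP 9.5.2.2.2 uses "Proc mi data=adefft out=monotone seed=1306528 nimpute=pctmissing" to start the control-based sensitivity analysis. That makes five calls in which the number of imputations, m, follows the percentage missing. A sixth call, "Proc mi data=monotone out=outmi seed=1306539 nimpute=1", runs once within each existing imputation and is correct as it stands.

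**Decision rule.** SAP 7.4 says that the 1-sided p-value "based on the results from combining all imputed datasets for overall inference (ie, from PROC MIANALYZE) will be compared with these stopping boundaries". The efficacy boundaries in SAP Table 3 are 0.0016 (about 122 patients) and 0.0245 (final).

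**Missing data.** Protocol 9.2 states: "Considering a nonevaluable rate of 10%, this study is planned to randomize approximately 270 patients". Protocol 8.4.12 says of patients who leave the study early: "The patient will be contacted via telephone on Day 29 to assess health status". Protocol 8.4.10 provides the same call for patients discharged early.

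**Age.** SAP 7.1.3.1 and 9.4.1 define age at first dose. The code notes in SAP 9.5.2.1 and 9.5.2.2.2 use age on Day 1.

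**The concern.** Multiple imputation adds simulation noise that shrinks as m grows. Tying m to the percentage missing makes m smallest when little is missing, so less missing data does not bring less noise. The seed is fixed, so the result can be repeated, but a p-value near 0.0016 or 0.0245 can still fall on one side or the other because of an arbitrary seed.

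The tipping-point analyses are more exposed. Their result is defined as the delta at which p crosses a threshold (1-sided 0.025 for survival, 2-sided 0.05 for the day counts), so they sit at a boundary by construction.

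On age, BSC-alone patients have no first dose, so the definition in SAP 9.4.1 cannot be applied to them. Age nevertheless enters the imputation and secondary models for both arms.

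**Working it through.** **1. The plan's own figures.** Inputs from SAP 9.3 and 7.4: 60% vs 80% survival, 1-sided 0.025, 2:1 allocation, pooled variance, one interim at 122 of 243.

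- Mean survival = (0.6 + 2 × 0.8)/3 = 0.7333.
- BSC patients, fixed design = [1.960 × √(1.5 × 0.7333 × 0.2667) + 1.2816 × √(0.24 + 0.16/2)]² / 0.2² = (1.0615 + 0.7250)² / 0.04 = 79.8, so 80 + 160 = 240.
- At 81 + 162 the power is 0.904 (fixed) and 0.903 (two looks). 243/0.9 = 270.
- O'Brien-Fleming-type spending at 122/243 gives 0.00156 at the interim and 0.02449 at the final look. The stated values are 0.0016 and 0.0245.

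The stated sample size, power and efficacy boundaries reproduce.

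**2. Noise in the pooled z.** To first order, its SD over seeds is √(f/m), with f the fraction of information missing, here close to the fraction of patients without survival status. If m = 100f, then √(f/100f) = 0.10, whatever f is, as long as m is at least 2. At m = 1000 and f = 0.10 it is √(0.10/1000) = 0.010.

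Simulation used the SAP imputation model, the MH difference with Sato variance, and Rubin's rules with a t reference. Status was assumed missing completely at random. For converged p-values at the boundary, the SD of the pooled z is:

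| Number of imputations | Look | 2% missing | 5% | 10% |
|---|---|---|---|---|
| Percentage missing, no minimum | final | 0.10 | 0.10 | 0.11 |
| Percentage missing, no minimum | interim | 0.10 | 0.11 | 0.12 |
| Assumed minimum 20 | final | 0.03 | 0.05 | 0.07 |
| Assumed minimum 20 | interim | 0.03 | 0.05 | 0.08 |
| 100 | final | 0.013 | 0.022 | 0.033 |
| 1000 | final | 0.004 | 0.007 | 0.010 |
| 1000 | interim | 0.004 | 0.007 | 0.011 |

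**3. On the p scale, 10% missing.** A converged p of 0.0245 has a 95% seed range of 0.015 to 0.040 (m = 10), 0.018 to 0.034 (m = 20) and 0.0235 to 0.0256 (m = 1000). A converged 0.0016 ranges over 0.0008 to 0.0035, 0.0010 to 0.0027 and 0.0015 to 0.0017.

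**4. Chance of a changed primary verdict.** To first order this is (density of z at the boundary) × SD × √(2/π).

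- Final look, 2% missing, n ≈ 265, 80% vs 60%: the SE of the difference is 0.0602, so mean z is 0.2/0.0602 = 3.32. The density at 1.969 is 0.160. Then 0.160 × 0.798 × SD = 0.4% (SD 0.03, minimum 20) or 1.3% (SD 0.10, no minimum).
- Final look, 10% missing, n = 243, m = 10: mean z 3.18, density 0.191, and 0.191 × 0.798 × 0.11 = 1.7%. Simulation also gives 1.7%, and 1.2% at m = 20.
- Less favourable cases by simulation, 10% missing, m = 10: 3.1% at the interim (80% vs 60%) and 3.4% at the final look if true survival is 73.5% vs 60%.

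**5. Operating characteristics.** Simulated null rejection was 2.4% to 2.8% for every m from 2 to 100. Power rises by only 0.2 to 0.4 points with m = 100 in place of the percentage missing.

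**6. Tipping point.** In 12 simulated datasets per scenario (converged p 0.012 to 0.0245), the average 5th-to-95th percentile seed range of delta was 1.5 log-odds at 5% missing with m = 5, against 0.17 with m = 1000. At 10% missing it was 0.8 with m = 10, against 0.15. With so few datasets these figures are indicative only.

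**The case against.** **The plan is valid as written.** The test holds its level, the seed is prespecified and the power gain is small. This stands, and it is why the point is an improvement and not a correction.

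**Little may be missing.** The ITT set keeps every randomised patient, and those who leave or are discharged early are telephoned on Day 29. This also stands: with no missing status the point vanishes. A reader might take the 10% in Protocol 9.2 as the expected rate of missing survival. The documents do not support that, because it is a nonevaluable allowance for sizing. Withdrawal and loss to follow-up are nevertheless foreseen (Protocol 7.2 and 7.3).

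**The noise need not be 0.10.** A reader might infer an SD of 0.10 at any non-zero missing rate. That goes too far. The software's minimum is not given in the documents. Without one, at about 1% missing or less, m would be 1 and there would be no between-imputation variance to pool.

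**Large crossing rates are conditional.** In datasets chosen because p lay just inside a boundary, the seed carried p across in 8% to 73% of repeats. That is not the chance that the trial is affected.

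**The interim may be specified elsewhere.** SAP 7.4.1 leaves further interim detail to the IDMC SAP, and SAP 9.5.2 calls its code basic. The number may be fixed there, but it is not fixed in these documents.

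**Conclusion.** The point holds as a small, nearly costless improvement. At 2% to 10% missing, and if no software minimum applies, the seed SD of the pooled z is about 0.10 at the final look and 0.10 to 0.12 at the interim. With an assumed minimum of 20 it is about 0.03 to 0.08. The primary verdict would change in about 0.4% to 3% of trials. The tipping-point deltas are affected by the same noise. These sizes assume that the percentage is that of patients without survival status, that status is missing completely at random, and the survival rates shown.

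The age mismatch is real but only a label. For dosed patients Day 1 is the date of first infusion, so the two definitions agree, and SAP 7 and 9.4.2 already define Day 1 for everyone else.

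Because age appears in most other models, a reader might infer that the primary MH test should be replaced by an age-adjusted one. The documents do not support that. The stratified test is valid and matches the randomisation, no age effect in ventilated patients is given, and any gain is therefore assumed. It would also change the primary method of an open-label trial. The age-adjusted difference in proportions in SAP 7.2.1 should stay a sensitivity analysis.

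**What to change.** - In SAP 9.5.2.1 (two calls), 9.5.2.2.1 (two) and 9.5.2.2.2 (the first call), replace `nimpute=pctmissing` by `nimpute=1000`. A value of 100 is not quite enough: for p-values very near a boundary, the seed still carried p across in up to 25% to 28% of repeats.
- Leave the `nimpute=1` step in SAP 9.5.2.2.2 unchanged.
- State the number in SAP 7.2.1.1 and in the IDMC SAP, so that both looks use it.
- In SAP 7.1.3.1 and 9.4.1, define age as age on Day 1 for every randomised patient, to match SAP 9.5.2.

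The cost is one option in five calls, slightly longer run time and two wording changes. No new data are needed, and the primary test, boundaries and sample size stay as they are.

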7.2.1. Primary Analysis

The primary efficacy endpoint is survival (based on all-cause mortality) at Day 29 and will be compared between the 2 treatment groups using a one-sided Mantel-Haenszel (MH) test of the difference in two proportions stratified by intubated or not intubated on Day 1 and a family-wise Type I error of 0.025. The estimated MH risk difference will be summarized along with the 2-sided 95% confidence interval (CI) using Mantel-Haenszel stratum weights ([Mantel, 1959](#)) and the Sato variance estimator. Handling of missing data for the primary analysis is described in [Section 7.2.1.1](#).

Survival will also be analyzed using the method of Kaplan and Meier (KM) and compared using a log-rank test stratified by intubated or not intubated on Day 1 as a sensitivity analysis. Hazard ratio and risk reduction will be summarized from a Cox proportional hazards model stratified by intubated or not intubated on Day 1. Confidence intervals (95%) will be presented for the survival estimate at Day 29 based on the complementary log-log transformation. Kaplan-Meier curves for both treatment groups will be produced.

A sensitivity analysis of the primary endpoint will also be performed using a 3-level categorical outcome of 3 (alive and discharged from the ICU); 2 (alive and in the ICU); or 1 (death). The 2 treatment groups will be compared using a proportional odds model with covariates for treatment group and the randomization stratification factor. If the assumption of proportional odds is rejected, a different approach will be considered.

Additional sensitivity analyses will include:

- A logistic regression with covariates for treatment group, age, sex, region, and randomization stratification factor. The estimate of the difference in survival proportions will be based on this logistic regression ([Ge, 2011](#)).

- A Cox proportional hazards model with covariates for treatment group, age, sex, region, and randomization stratification factor. The treatment group hazard ratio and risk reduction from the model will be summarized.

A summary table and listing of patients who died during the study will also be provided with reason for death, where available.

An interim analysis of the primary endpoint will also be conducted as described in [Section 7.4](#).

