9.3. Sample Size, Power, and Randomization

A sample size of 243 patients (162 ravulizumab + BSC, 81 BSC alone) is required to ensure at least 90% power and detect an improvement in survival from 60% in the BSC alone group to 80% in the ravulizumab + BSC group at Day 29.

This sample size calculation was performed in EAST 6.5 and assumes:

- 1-sided Z-test of the difference in 2 proportions,
- Type I error = 0.025,
- Pooled variance,
- 2:1 randomization on the 2 treatment groups,
- One interim analysis at 50% information which will be after collecting primary efficacy data on approximately 122 patients. The early stopping boundaries for efficacy and futility (non-binding) will be constructed using α -spending function as Lan-DeMets spending function with O'Brien-Fleming flavor and β -spending function as Gamma(-4) ([Lan, 1983](#); [Hwang, 1990](#)).

Considering a nonevaluable rate of 10%, this study is planned to randomize approximately 270 patients (180 ravulizumab + BSC, 90 BSC alone).

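### The primary tipping-point analysis looks for reversal at the family-wise level of 0.025 instead of the Table 3 boundary in force, so it finds the tipping delta too late: trivially at the final analysis, materially after an interim stop

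*SAP*

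**What the plan says.** SAP Section 7.2.1 sets up the primary comparison as a one-sided Mantel-Haenszel test, "stratified by intubated or not intubated on Day 1 and a family-wise Type I error of 0.025". That level is shared between one interim and one final analysis.

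SAP Section 7.4 divides it. For the interim: "The p-value efficacy and futility boundaries for the interim analysis with 122 patients are 0.0016 and 0.5016". The last row of Table 3 reads "Final (243 patients) 0.0245 0.0245" (efficacy, then futility). The one-sided p-value pooled over the imputed datasets "will be compared with these stopping boundaries".

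SAP Section 7.2.1.1 describes the tipping-point analysis. Imputed survival in the ravulizumab arm is made progressively worse by delta until a positive primary result no longer holds. SAP Section 9.5.2.1 turns this into a numerical rule: the tipping point is "the value of delta for which the nominal 1-sided p-value crosses 0.025".

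SAP Sections 7.2.1 and 7.2.1.4 also ask for a two-sided 95% confidence interval around the primary risk difference.

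**The concern.** The two sections disagree about when a positive conclusion ends. Section 7.4 says it ends at 0.0245 (final) or 0.0016 (interim). Section 9.5.2.1 says it ends at 0.025. The latter calls its p-value nominal, which is how Section 7.4 describes the p-value set against the boundaries, but it supplies the family-wise level as the cut.

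The error runs in one direction. Any delta that leaves the p-value between the boundary and 0.025 is counted as leaving the conclusion intact, although that result would not have been declared positive. The reported tipping delta is therefore too large, and the conclusion looks more robust to missing data than it is.

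SAP Section 4.2 says the added missing-data sensitivity analyses, the tipping point among them, came from health-authority feedback, so the threshold is likely to be read closely.

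**Working it through.** **Inputs.** Overall one-sided alpha 0.025 (SAP 7.2.1). Lan-DeMets O'Brien-Fleming spending, boundaries 0.0016 and 0.0245 (SAP 7.4). Timing: "One interim analysis at 50% information which will be after collecting primary efficacy data on approximately 122 patients" (SAP 9.3). Planned 162 versus 81 patients, survival 80% versus 60% (SAP 9.3).

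**Step 1: reproduce Table 3.** The spending function is α(t) = 2[1 − Φ(z₀.₉₈₇₅/√t)].
- At t = 122/243 = 0.502, the interim boundary is 0.00156, which rounds to 0.0016.
- Solving the bivariate normal with correlation √t for an overall 0.025 gives a final boundary of 0.02449, which rounds to 0.0245.
- At t = 0.5 the pair is 0.00153 and 0.02450.

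So 0.0245 is no misprint, and Section 9.5.2.1 is the text to change.

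**Step 2: the gap at the final analysis.** One-sided 0.025 is z = 1.9600; 0.0245 is z = 1.9686.
- Unpooled SE = √(0.6×0.4/81 + 0.8×0.2/162) = 0.0629. Risk differences at the two cuts: 1.9600 × 0.0629 = 0.1232 and 1.9686 × 0.0629 = 0.1237. Gap 0.0005.
- Pooled SE: average survival 0.7333, SE = √(0.7333×0.2667×(1/81 + 1/162)) = 0.0602. Gap again 0.0005.

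That is about 0.05 percentage points.

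**Step 3: the gap after an interim efficacy stop.** With 122 patients split 2:1 (40.67 versus 81.33), SE = √(0.24/40.67 + 0.16/81.33) = 0.0887.
- At 0.025: 1.9600 × 0.0887 = 0.174.
- At 0.0016 (z = 2.9478): 2.9478 × 0.0887 = 0.261.

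The gap is 0.261 − 0.174 = 0.088, or nearly 9 percentage points.

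**Step 4: what this means for delta.** The documents give no expected rate of missing survival status, so this step uses an assumed range. If a fraction m of ravulizumab patients is missing and their imputed survival probability falls by d, the arm's survival falls by about m × d (SE held fixed).

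| Assumed m | Final: 0.0005/m | Interim stop: 0.088/m |
|---|---|---|
| 5% | 0.01 | 1.76 (more than the whole probability scale) |
| 10% | 0.005 | 0.88 |

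At the final analysis the overstatement is a percentage point or less of imputed survival. After an interim stop, a result that only just crossed 0.0016 could lose that boundary under a small shift and still not reach 0.025 under almost any shift.

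**The case against.** The strongest reply is that the tipping point decides nothing. It is a sensitivity analysis, the decision thresholds are in Table 3, and Section 7.4 says which p-value is compared with them. All of that stands.

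It is also fair that the final-analysis gap is below the noise of the method. Section 9.5.2.1 ties the number of imputations to the percentage missing. In a simplified simulation (unstratified, 3% to 10% missing assumed, results near p = 0.025) the pooled p-value varied between seeds with a standard deviation of about 0.005 to 0.007, ten or more times the 0.0005 gap. The SAP fixes the seed and gives no delta step, so the difference may not show on the grid used. This reply does not reach the interim case, where the two cuts are 0.0016 and 0.025.

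Three stronger readings are tempting, and the documents do not support them.

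- **That Type I error is inflated.** Using 0.025 as the final cut after a 0.0016 interim would give an overall 0.0255, against 0.0250 with 0.0245. But the plan does not specify that procedure: 0.025 is labelled family-wise in Section 7.2.1 and overall in Section 7.4.
- **That the tipping analysis could contradict a failed primary test.** It starts from a positive result, so it can only find the reversal late.
- **That the 95% interval is wrong.** It can exclude zero when the final test fails. For example, 124/162 versus 52/81 survivors (unstratified Wald) gives p = 0.0247 and a 95% lower limit of +0.0003, whereas the matching 95.1% interval (1 − 2 × 0.0245) has a lower limit of −0.0002. But no section uses the interval as a decision rule, and a nominal 95% interval is a legitimate summary.

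**Conclusion.** The point holds as an inconsistency between SAP Sections 9.5.2.1 and 7.4. The tipping rule uses the family-wise level where the boundary in force belongs, and so overstates the tipping delta. The size is about 0.05 percentage points of risk difference at the final analysis, which is negligible. It is about 9 percentage points (0.26 against 0.17) if the trial stops for efficacy at the interim, which is material to how robust the result would appear.

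The interim figures assume 122 patients in a 2:1 split, standard errors at the planning survival rates, and a tipping analysis run on the data that triggered the stop. Later data from patients already enrolled would change them. The tipping rule for the ventilation, ICU and hospitalization endpoints in SAP 9.5.2.2.1 uses two-sided 0.05, which matches the level at which those endpoints are tested, and is not affected.

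**What to change.** In SAP Section 9.5.2.1, replace 0.025 in the tipping-point rule with the Table 3 efficacy boundary in force at the analysis being reported: 0.0245 (or its recomputed value) at the final analysis, 0.0016 if the trial stopped for efficacy at the interim.

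Optionally, add a phrase in SAP Section 7.2.1 labelling the 95% interval as nominal and unadjusted for the interim look.

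The cost is one line, or two with the optional label. Nothing changes in design, conduct, data collection, the primary test, sample size or power. It is best done before unblinded results are seen, so that nobody has to argue afterwards about which threshold was prespecified.
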